### **6.2.5. Sensitivity Analyses for the Primary Efficacy Endpoints**

#### **6.2.5.1. Clinical Remission by PRO2 (EU-specific)**

Sensitivity analysis will be conducted according to the composite estimand 2 specified in Section 6.2.3.

The multivariate imputation by chained equations (MICE) {Azur 2011} through regression model will be used to impute each missing subscore in PRO2. For Induction Studies, each subscore in PRO2 at baseline, Weeks 2, 4, 6, and 10, treatment, and stratification factors will be included in the imputation model using the Full Analysis Set. For the Maintenance Study, each subscore in PRO2 at maintenance baseline, Weeks 14, 20, 26, 34, 42, 50, and 58, treatment, and stratification factors will be included in the imputation model using the Full Analysis Set among the subjects from Induction Cohorts A and B combined being treated with the same dose of filgotinib.

For each imputed dataset, the clinical remission status by PRO2 will be derived. The subjects who met treatment failure criteria or prematurely discontinued from the study without available result from the study will be set as not achieving clinical remission in each imputed dataset. The parameters of interest for each imputed dataset will be estimated using a similar method as the primary approach. The results from multiple imputations will be combined using Rubin's rule {Rubin 1987}.

In addition, tipping point analysis with delta-adjusting pattern-mixture approach {Ratitch 2013} will be conducted to assess the robustness of analysis result under the MNAR (missing not at random) assumption. The proposed method will perform a series of analyses after adjusting for stratification factors with a range of different values of the shift parameter  $\delta$  applied to the imputed datasets at which the conclusion about the statistical significance of result will be altered. Specifically, the analysis is characterized by two-dimensional sequences (one sequence associated with missing data in the placebo group and the other associated with missing data in the filgotinib group). In the first step for both sequences, the missing data in both treatment groups are imputed under the missing at random (MAR) assumption. For each subsequent step of the placebo sequence, the missing data are imputed assuming incrementally more favorable than in the previous step of that sequence while holding the shift parameter constant in the filgotinib

group. Similarly, for each subsequent step of the filgotinib group sequence, the missing data are imputed assuming incrementally less favorable than in the previous step of that sequence while holding the shift parameter constant in the placebo group.

[Appendix 8](#) provides sample SAS model statements for the tipping point analysis. Each  $\delta$  value is classified as either “altering the statistical significance conclusion” or “keeping the statistical significance conclusion unchanged.” The tipping points that alter the statistical significance conclusion will be provided. The same analysis method for the primary analysis as specified in [Section 0](#) will be applied when analyzing the adjusted data generated under different  $\delta$  values.

#### 6.2.5.2. Clinical Remission by CDAI (other: non-EU)

Sensitivity analysis will be conducted according to the composite estimand 2 specified in [Section 6.2.3](#).

The multivariate imputation by chained equations (MICE) [{Azur 2011}](#) through regression model will be used to impute the missing CDAI. If the subscore for at least 1 component is missing, then the CDAI is considered missing. For Induction Studies, the CDAI at baseline, Weeks 2, 4, 6, and 10, treatment, and stratification factors will be included in the imputation model using the Full Analysis Set. For the Maintenance Study, the CDAI at maintenance baseline, Weeks 14, 20, 26, 34, 42, 50, and 58, treatment, and stratification factors will be included in the imputation model using the Full Analysis Set among the subjects from Induction Cohorts A and B combined being treated with the same dose of filgotinib.

For each imputed dataset, the clinical remission status by CDAI will be derived. The subjects who met treatment failure criteria or prematurely discontinued from study without available result from study will be set as not achieving clinical remission in each imputed dataset. The parameters of interest for each imputed dataset will be estimated using a similar method as the primary approach. The results from multiple imputations will be combined using Rubin’s rule [{Rubin 1987}](#).

In addition, tipping point analysis with delta-adjusting pattern-mixture approach [{Ratitch 2013}](#) will be conducted to assess the robustness of analysis result under the MNAR (missing not at random) assumption. The proposed method will perform a series of analyses after adjusting for stratification factors with a range of different values of the shift parameter  $\delta$  applied to the imputed datasets at which the conclusion about the statistical significance of result will be altered. Specifically, the analysis is characterized by two-dimensional sequences (one sequence associated with missing data in the placebo group and the other associated with missing data in the filgotinib group). In the first step for both sequences, the missing data in both treatment groups are imputed under the missing at random (MAR) assumption. For each subsequent step of the placebo sequence, the missing data are imputed assuming incrementally more favorable than in the previous step of that sequence while holding the shift parameter constant in the filgotinib group. Similarly, for each subsequent step of the filgotinib group sequence, the missing data are imputed assuming incrementally less favorable than in the previous step of that sequence while holding the shift parameter constant in the placebo group.

Appendix 8 provides sample SAS model statements for the tipping point analysis. Each  $\delta$  value is classified as either “altering the statistical significance conclusion” or “keeping the statistical significance conclusion unchanged.” The tipping points that alter the statistical significance conclusion will be provided. The same analysis method for the primary analysis as specified in Section 6.2.4 will be applied when analyzing the adjusted data generated under different  $\delta$  values.

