**Table 6-1. Definitions of Selected Efficacy Endpoints**

Study	Type	Endpoint	Definition
Induction	EU: secondary Non-EU: Co-primary	Clinical remission by CDAI at Week 10	CDAI score < 150 points at Week 10
Induction	Co-primary	Endoscopic response at Week 10	≥ 50% reduction from baseline in total SES-CD score at Week 10 based on central reading
Induction	EU: co-primary Other: Secondary	Clinical remission by PRO2 at Week 10	Abdominal pain score ≤ 1 (on a scale of 0 to 3) and liquid or very soft stool (Bristol stool scale type 6 or 7) frequency ≤ 3 at Week 10
Induction	Secondary	Clinical response by CDAI at Week 10	Reduction in CDAI score from Induction baseline by at least 100 points or CDAI score < 150 at Week 10
Induction	CCI	CCI	CCI
Induction	EU: Secondary Non-EU: CCI	Both clinical remission by PRO2 and endoscopic response at Week 10	Clinical remission by PRO2 and endoscopic response at Week 10 combined into a single endpoint on a patient level
Induction	CCI	CCI	CCI
Induction	CCI	CCI	CCI
Induction	CCI	CCI	CCI
Maintenance	Co-primary	Clinical remission by CDAI at Week 58	CDAI score < 150 points at Week 58

Study	Type	Endpoint	Definition
Maintenance	Co-primary	Endoscopic response at Week 58	≥ 50% reduction from Induction baseline in total SES-CD score at Week 58 based on central reading
Maintenance	Secondary	Clinical remission by PRO2 at Week 58	Abdominal pain score ≤ 1 (on a scale of 0 to 3) and liquid or very soft stool (Bristol stool scale type 6 or 7) frequency ≤ 3 at Week 58
Maintenance	Secondary	Clinical response by CDAI at Week 58	Reduction in CDAI score from Induction baseline by at least 100 points or CDAI score < 150 at Week 58
Maintenance	Non-EU: secondary	Sustained clinical remission by CDAI at Weeks 10 and 58	Clinical remission by CDAI at both Week 10 and Week 58
Maintenance	Non-EU: secondary	6-month Corticosteroid-free clinical remission by CDAI at Week 58	Clinical remission by CDAI with no corticosteroid use for the indication of CD for at least 6 months prior to Week 58 among subjects who are on corticosteroid at maintenance baseline (baseline of Maintenance Study). Subjects who weaned off steroids but required re-initiation within 6 months prior to Week 58 assessment will be considered to have not met this endpoint.
Maintenance	Secondary	Sustained clinical remission by PRO2 at Weeks 10 and 58	Clinical remission by PRO2 at both Week 10 and Week 58

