### 6.1.3. COVID-19 Impact on Primary Efficacy Endpoints

The number of subjects with the following categories due to COVID-19 will be summarized by treatment at Week 10 for Induction Studies and at Week 58 for Maintenance Study.

- Missed visit (including out of efficacy analysis window, as defined in Section 3.8.2)
- Delayed visit (occurring after the upper limit of the efficacy analysis visit window, as defined in Section 3.8.2)

For CDAI assessments, the number of subjects with the following categories due to COVID-19 will be summarized by treatment at Week 10 for Induction Studies and at Week 58 for Maintenance Study.

- Number of missed components (including out of analysis window, as defined in Section 3.8.2)
- Number of delayed components (occurring after the upper limit of the analysis visit window, as defined in Section 3.8.2)
- Number of virtually or locally conducted components. Only the following 3 components may be conducted virtually or locally: use of anti-diarrheal medications, hematocrit (from local laboratory), and weight (at home).

For SES-CD assessments, the number of subjects with the following categories due to COVID-19 will be summarized by treatment at Week 10 for Induction Studies and at Week 58 for Maintenance Study.

- Missed ileocolonoscopy (including out of analysis window, as defined in Section 3.8.2)

- Delayed ileocolonoscopy (occurring after the upper limit of the analysis visit window, as defined in Section 3.8.2)

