#### 6.2.5.3. Endoscopic Response

Sensitivity analysis will be conducted according to the composite estimand 2 specified in Section 6.2.3.

The MICE {Azur 2011} through regression model will be used to impute the missing segmental subscores. For Induction Studies, the segmental score at baseline and Week 10, treatment, and stratification factors will be included in the imputation model using the FAS. For the Maintenance Study, the segmental score at maintenance baseline and Week 58, treatment, and stratification factors will be included in the imputation model using the Full Analysis Set among the subjects from Induction Cohorts A and B combined being treated with the same dose of filgotinib.

For each imputed dataset, the percentage change from Induction baseline in the total SES-CD score will be calculated for each subject and the endoscopic response status will be derived. The subjects who met treatment failure criteria or prematurely discontinued from study without available result will be set as non-responders in each imputed dataset. The parameters of interest for each imputed dataset will be estimated using a similar method as the primary approach. The results from multiple imputations will be combined using Rubin’s rule {Rubin 1987}.

In addition, tipping point analysis with delta-adjusting pattern-mixture approach {Ratitch 2013} will be conducted to assess the robustness of analysis result under the MNAR (missing not at random) assumption (see Section 6.2.5.1).

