**Figure 13-2. Selection of Diary Data for the Calculation at Post-Screening Visits**

**Table 13-5. Calculation of CDAI Patient-Reported Outcome Components and PRO2 Scores at Post-Screening Visits**

Example	Diary Day Looking Backwards from Visit Date (V-Day)										Days for Calculation	Sum of 7 Days (CDAI Patient-Reported Component)	Average of 7 Days (PRO2)
	-10	-9	-8	-7	-6	-5	-4	-3	-2	-1			
Diary Subscore 1	1	2	2	M	0	1	2	2	1	X	-2,-3,-4,-5,-6,-8,-9	10.0	1.4
Diary Subscore 2	M	M	1	M	X	IL	2	2	1	M	-2,-3,-4,-8	10.5	1.5
Diary Subscore 3	M	M	1	X	IL	M	M	2	1	M	-2,-3,-8	Missing	Missing
Diary Subscore 4	0	M	2	2	1	0	M	2	X	IL	-3,-5,-6,-7,-8,-10	8.2	1.2

M = Missing; IL = Ileocolonoscopy day; X = non-evaluable (due to preparation for ileocolonoscopy).

Days are named relative to visit date (V-Day 1), where V-Day -1 is the day prior to V-Day 1.

Rounding of subscores into one decimal place is for displaying purpose only. When calculating the total CDAI scores, the subscores will not be rounded.

- 4) The CDAI total score for a specific visit is based on a weighted sum (rounded to the nearest integer) of all 8 components. The CDAI total score will be set to 0 in the case the calculation leads to a CDAI total score of < 0. Each component will be selected within the analysis window as defined in
- 5) If subjects have 3 or more of the 8 CDAI components missing, then the subjects will be considered as having insufficient data to determine response status and their total CDAI score will be considered missing. If at least 1 out of the 6 complications under the complication component is missing, then the complication component will be considered missing.

- a) If subjects have 1 or 2 CDAI components missing, then the missing component will be imputed by the LOCF method using the previous valid component score calculated from the most recent analysis visit (ie, use the component score from Week 6 for missing component at Week 10, or use the component score from Week 50 for missing component at Week 58. Scores from other post Induction baseline visits will not be used). If the component score from the most recent analysis visit is also missing, the missing value will be imputed with the corresponding component score at Induction baseline.

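### The CDAI multiple-imputation sensitivity analysis ignores the components observed at Week 10 or Week 58, so an imputed total can contradict data already collected

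*SAP*

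**What the plan says.** SAP 6.2.5.2 carries out composite estimand 2 for CDAI remission. Its trigger is "If the subscore for at least 1 component is missing, then the CDAI is considered missing". For the Induction Studies, "the CDAI at baseline, Weeks 2, 4, 6, and 10, treatment, and stratification factors will be included in the imputation model"; the Maintenance Study uses the same structure with totals from maintenance baseline to Week 58. No component enters the model and no bound on the imputed total is stated. Remission status is then derived in each imputed dataset. The only override is that subjects who "met treatment failure criteria or prematurely discontinued from study without available result from study will be set as not achieving clinical remission".

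Three other places in the SAP treat partial data differently:

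- **Primary CDAI analysis (6.1.1, Table 6-4).** Observed components are kept. One or two missing components are filled by LOCF, and the total is missing only when three or more are missing.
- **PRO2 (6.2.5.1).** Imputation "through regression model will be used to impute each missing subscore in PRO2".
- **SES-CD (6.2.5.3).** Imputation "through regression model will be used to impute the missing segmental subscores".

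Table 6-5, which defines estimand 2 for CDAI, sends a missing CDAI to imputation but does not say when a CDAI counts as missing. A component is easily lost. Appendix 3, item 5, states: "If at least 1 out of the 6 complications under the complication component is missing, then the complication component will be considered missing".

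**The concern.** A subject still in the study with seven of eight components recorded at Week 10 is handled as if nothing had been recorded. If those seven already place the total above the remission threshold, "CDAI score < 150 points at Week 10", the outcome is known, but the model is free to draw a total below 150. The same mechanism can turn a subject who is in remission into a failure.

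This is the planned multiple-imputation check of the non-EU clinical co-primary. A reader would expect it to show whether the component LOCF rule drives the primary result. It changes much more than the missing component, so a difference from the primary analysis could come either from the LOCF assumption or from discarding observed data.

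**Working it through.** **1. Planned rates.** The only stated figure tied to this endpoint is the 97% induction power (SAP 1.3: 220 per arm, two-sided 0.05, CDAI remission 45% v 25%, endoscopic response 25% v 10%). A two-proportion calculation gives 0.9937 × 0.9869 = 0.981, or 0.974 with continuity correction. The plan's figure is reproduced closely enough to use its rates below.

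**2. When observed components settle the outcome.** In SAP Table 13-1, seven components are zero or positive and weight cannot fall below -10. Hence:

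- weight observed: total ≥ observed partial sum, so a sum of at least 150 excludes remission;
- weight missing: total ≥ observed partial sum - 10, so a sum of at least 160 excludes remission.

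Example: four liquid stools a day, pain 2 and well-being 2 give (28 × 2) + (14 × 5) + (14 × 7) = 56 + 70 + 98 = 224 from the diary alone. Even with weight missing, the total is at least 214.

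**3. Chance that one draw contradicts this.** The total is rounded to an integer, so remission means a raw total below 149.5. For predicted mean μ and residual SD σ (both assumed), P = Φ((149.5 - μ)/σ).

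| μ | σ = 50 | σ = 70 | σ = 90 |
|---|---|---|---|
| 200 | 16% | 24% | 29% |
| 220 | 8% | 16% | 22% |
| 250 | 2% | 8% | 13% |

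**4. Averaged over subjects.** The documents give no CDAI SD or visit correlation, so these are assumptions. Two simulations with different set-ups were used, both with the Week 6 total as the only CDAI predictor.

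| Set-up | Ruled-out subject drawn as remitter | Remitter drawn as failure |
|---|---|---|
| Hematocrit missing at random, SD 70 or 90, correlation 0.5 to 0.85, arms pooled | 10 to 27% | 22 to 52% (true total below 119) |
| Complications and mass missing, SD 100, correlation 0.6 to 0.8, 200 mg at 45% | 22 to 33% | 31 to 42% |
| Same, placebo at 25% | 13 to 19% | 44 to 59% |

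Adding Weeks 2 and 4 at equal correlation lowers the first error in the second set-up to 18 to 28% (200 mg) and 10 to 16% (placebo).

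**5. Net effect on the arm rate, among partly observed subjects.** At 200 mg, false remitters add about 55% × 22 to 33% = 12 to 18 points, and false failures remove 45% × 31 to 42% = 14 to 19 points. On placebo the figures are 75% × 13 to 19% = 10 to 14 points and 25% × 44 to 59% = 11 to 15 points. The small remainder is mostly subjects whose observed sum is below 150 but whose full total is not. With components missing completely at random, the imputed rates return to about 45% and 25%. In an illustrative case where missingness depended on the discarded components, the arm rates rose by about 1 to 2 points.

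**6. Size in the trial.** Suppose 1 to 10% of an arm is ruled out but partly missing, and 10 to 25% of their draws are remissions. Counting that error alone, the arm rate rises by 1% × 10% = 0.1 point to 10% × 25% = 2.5 points, or 0.2 to 5.5 of 220 subjects. Power for the CDAI comparison stays near 99% if both arms are affected equally. At the 10%/25% extreme it is 97.1% if only placebo is affected and 99.9% if only filgotinib is.

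**The case against.** The strongest defence is that multiple imputation targets the arm rate, not each subject's status, and step 5 shows almost no net bias under completely random missingness. Section 6.2.3.2 assigns component-level handling to estimand 1, so a subject-level estimand 2 looks like a deliberate choice. A tipping-point analysis is also planned. All of this limits the size of the problem. It does not justify discarding recorded components, and it does not hold if missingness is related to them. The Appendix 8 tipping-point code models the binary response on treatment and three strata only, so it brings neither the components nor earlier CDAI values back in.

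Several stronger readings are tempting but not supported:

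- **Ruled-out subjects are routinely imputed as remitters.** This happens in a minority of draws. Treatment failures and discontinuations without a result are fixed as non-remitters.
- **Every virtual Week 10 or Week 58 CDAI is discarded.** Section 6.1.3 limits what can be done virtually or locally to anti-diarrheal use, hematocrit and weight. However, Appendix 3 selects each component within the analysis window, and both visits schedule an ileocolonoscopy. An on-site assessment in the window could supply complications and abdominal mass.
- **It also undermines the EU key secondary.** Section 6.2.5.2 is headed non-EU, and 6.3.2 specifies only the primary method for key secondary endpoints.
- **It favours filgotinib.** The errors run both ways, and the net direction is not fixed.

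The objection to a full model of eight components at every visit is sound. That would be 8 × 8 = 64 scores for a planned 60 + 120 = 180 maintenance subjects.

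**Conclusion.** The concern holds in a limited form. As written, the CDAI imputation can contradict components already recorded, in both directions, and it departs without a stated reason from the PRO2 and SES-CD imputations and from the primary CDAI rule. The contradiction follows from the component bounds and needs no assumption. The error rates rest on assumed SDs, correlations and missingness patterns. The trial-level effect rests on an assumed share of partly missing CDAI, for which the documents give no figure; it is probably small. Only the non-EU sensitivity analysis (composite estimand 2) is affected. The primary test is not. The main cost is to interpretation: the analysis cannot show whether the component LOCF rule matters.

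**What to change.** Replace the trigger sentence in 6.2.5.2. At Week 10 and Week 58, impute only the missing component or components, within their bounds (weight at least -10, all others at least 0). Condition on the components observed at that visit, CDAI totals at the other listed visits, treatment and strata, and then sum. Impute an unrestricted total only when all components are missing. State the same definition of missing in Table 6-5.

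The score variables rise from 5 to 8 + 4 = 12 for induction and from 8 to 8 + 7 = 15 for maintenance. That is a somewhat larger model with modest extra programming and no new data.

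A simpler alternative keeps the total-score model and bounds each imputed total below by the observed partial sum (minus 10 if weight is missing). It removes the impossible remissions but does not reduce the false failures, so the cancellation in step 5 is lost. With the second set-up's error rates, imputed remission among partly observed subjects would be at most about 45% × (1 - 0.31 to 0.42) = 26 to 31% at 200 mg, and 25% × (1 - 0.44 to 0.59) = 10 to 14% on placebo. The component-level version is therefore preferable. If the bound is used, its conservative direction should be stated.

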#### 6.2.5.3. Endoscopic Response

Sensitivity analysis will be conducted according to the composite estimand 2 specified in Section 6.2.3.

The MICE {Azur 2011} through regression model will be used to impute the missing segmental subscores. For Induction Studies, the segmental score at baseline and Week 10, treatment, and stratification factors will be included in the imputation model using the FAS. For the Maintenance Study, the segmental score at maintenance baseline and Week 58, treatment, and stratification factors will be included in the imputation model using the Full Analysis Set among the subjects from Induction Cohorts A and B combined being treated with the same dose of filgotinib.

For each imputed dataset, the percentage change from Induction baseline in the total SES-CD score will be calculated for each subject and the endoscopic response status will be derived. The subjects who met treatment failure criteria or prematurely discontinued from study without available result will be set as non-responders in each imputed dataset. The parameters of interest for each imputed dataset will be estimated using a similar method as the primary approach. The results from multiple imputations will be combined using Rubin’s rule {Rubin 1987}.

In addition, tipping point analysis with delta-adjusting pattern-mixture approach {Ratitch 2013} will be conducted to assess the robustness of analysis result under the MNAR (missing not at random) assumption (see Section 6.2.5.1).

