**1.2.4. Schedule of Assessments**

Efficacy will be assessed primarily through CDAI, PRO2, and Simple Endoscopic Score for Crohn's Disease (SES-CD). CDAI and PRO2 will be assessed at Screening, Weeks 2, 4, 6, 10, 14, 20, 26, 34, 42, 50, and 58, and ET. SES-CD will be assessed at Screening, Week 10, and Week 58.

For additional details, please see the Schedule of Assessments in [Appendix 1](#).

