##### **3.8.1.2. Maintenance Study**

The First Dosing Date of Maintenance Study is defined as the date when subjects take the first dose of Maintenance Study drug, as recorded in the Study Drug Administration eCRF.

The Last Dosing Date of Maintenance Study is defined as the date when subjects take the last dose of Maintenance Study drug as recorded in the Study Drug Administration eCRF.

Maintenance Study Day (M-Day) will be calculated from the First Dosing Date of Maintenance Study and derived as:

- For days on or after First Dosing Date of Maintenance Study:  
Assessment Date – First Dosing Date + 1
- For days prior to First Dosing Date of Maintenance Study:  
Assessment Date – First Dosing Date

Therefore, M-Day 1 is the first dosing date of the Maintenance Study.

Re-randomization baseline (henceforth referred to as maintenance baseline) is defined as the last available observation on or prior to the first dosing date of the Maintenance Study. Maintenance baseline will be considered the baseline of Maintenance Study, unless otherwise specified.

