### Endoscopic Response

For each of the 5 bowel segments, if the subscore of a segment is missing at baseline, this segment will not be included in the calculation of the total SES-CD for all the visits for the purpose of evaluating endoscopic response. If the subscore of a segment is observed at baseline but missing at Week 10 (or Week 58), it will be imputed using a score of 12 (worst subscore from the sum of the 4 variables in a segment). This is the primary approach to impute missing data in a segment.

If the percentage reduction from baseline in total SES-CD is  $\geq 50\%$ , then the subject will be defined as achieving endoscopic response.

If the above criteria are not met, the subject will be considered as not achieving endoscopic response.

CCI

CCI

CCI

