**Table 6-7. Composite Estimand 2 (Sensitivity Analysis) for Endoscopic Response**

Attributes	Composite Estimand 2
Treatment	Filgotinib 200 mg, filgotinib 100 mg, or placebo
Population	Full Analysis Set as defined in Section 3.1.2
Segment-level outcome to be measured	SES-CD subscore for each segment at baseline and Week 10 for Induction Studies and at Week 58 for Maintenance Study
Subject-level outcome to be measured	Endoscopic response status (Yes/No) at Week 10 for Induction Studies and at Week 58 for Maintenance Study  If the percentage reduction of total SES-CD from Induction baseline is $\geq 50\%$ , then the subject will be defined as achieving endoscopic response at

	Week 10 or at Week 58, respectively. If the above responder criterion is not met, the subject will be considered as not achieving endoscopic response. If total SES-CD is missing, then data will be analyzed using MICE as outlined in section 6.2.5.
Measure of intervention effect & handling of missing data due to intercurrent events (segment-level outcome)	All segments will be included in the total SES-CD calculation regardless of being missing or not.
Measure of intervention effect & handling of missing data due to intercurrent events (subject-level outcome)	Subject who met treatment failure criteria (ie, take potentially effective medications rather than study treatment as defined in Appendix 6 ) or prematurely discontinued from study without available assessment result is considered a non-responder.
Population-level summary measure	Difference in proportions in endoscopic response, comparing a filgotinib dose group to placebo group

SES-CD = Simple Endoscopic Score for Crohn's Disease

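### The Maintenance imputation model for endoscopic response omits the Induction-baseline segment scores that define the endpoint, and Table 6-7 makes no exception for surgically absent bowel

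*SAP*

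**What the plan says.** **Endpoint.** SAP Table 6-1 defines Week 58 endoscopic response as at least a 50% reduction in total SES-CD from Induction baseline. After imputation, SAP 6.2.5.3 keeps that reference: "the percentage change from Induction baseline in the total SES-CD score will be calculated for each subject".

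**Primary handling of segments.** SAP 6.1.2 states: "if the subscore of a segment is missing at baseline, this segment will not be included in the calculation of the total SES-CD". The exclusion applies at all visits. A segment seen at baseline but missing later is scored 12 (also Table 6-6).

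**Sensitivity handling.** Table 6-7 (composite estimand 2) reverses the baseline rule: "All segments will be included in the total SES-CD calculation regardless of being missing or not". In 6.2.5.3, MICE "through regression model will be used to impute the missing segmental subscores".

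**Imputation models.** For Induction, "the segmental score at baseline and Week 10, treatment, and stratification factors will be included in the imputation model using the FAS". For Maintenance, "For the Maintenance Study, the segmental score at maintenance baseline and Week 58, treatment, and stratification factors will be included in the imputation model". Maintenance baseline "is defined as the last available observation on or prior to the first dosing date of the Maintenance Study" (SAP 3.8.1.2), and "SES-CD will be assessed at Screening, Week 10, and Week 58" (SAP 1.2.4), so for SES-CD it is normally the Week 10 value.

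**Surgery.** Protocol 4.2.2, criterion 10, excludes total or subtotal colectomy and stomas. It does not list ileocaecal or limited segmental resection. SAP 5.2 tabulates prior surgery for Crohn's disease.

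**The concern.** There are two gaps in one sensitivity analysis.

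First, the Week 58 score is imputed without the value it will be compared with. If Week 58 scores depend on Induction baseline beyond what Week 10 conveys, the imputed scores lose that link, and derived response is misclassified more often than it need be. There is also an unspecified step. Estimand 2 requires every segment in the total, but a segment missing at Induction baseline is not a variable in the Maintenance model, so its contribution to the denominator at Week 58 is left to the programmer.

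Second, the SAP does not distinguish a segment that was not examined from one that no longer exists. For the former, imputing a score is meaningful. For the latter, the score has no referent, yet it would enter both the numerator and the denominator of the percentage change.

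At stake is how well this analysis serves as a check on the worst-score rule for missing segments.

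**Working it through.** **Plan's own figure.** No stated number rests on this analysis. The only one tied to the Week 58 endoscopic endpoint is the 94% Maintenance power (60 against 120 subjects, 20% against 50%). A continuity-corrected normal calculation gives 0.9755 per endpoint, and 0.9755² = 95.2%, close to the stated value. Nothing below changes it.

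**Model against endpoint (Maintenance)**

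| Quantity | In the listed model? | Used to derive response? |
|---|---|---|
| Induction-baseline segment scores | No | Yes, as the reference |
| Maintenance baseline (normally Week 10) | Yes | No |
| Week 58 segment scores | Yes | Yes |

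**Counting a segment absent at baseline.** Let the observed segments total B at baseline and W at follow-up, and let the added segment be imputed as b and w. The reduction changes from 1 − W/B to 1 − (W + w)/(B + b). For b above 0, this is the average of the two separate reductions weighted by B and b, so it is pulled toward the imputed segment's own reduction.

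- Observed 12 to 6: 1 − 6/12 = 50.0%, responder. Add 3 to 3: 1 − 9/15 = 40.0%, non-responder.
- Observed 8 to 3: 1 − 3/8 = 62.5%, responder. Add 6 to 5: 1 − 8/14 = 42.9%, non-responder.
- Observed 12 to 7: 1 − 7/12 = 41.7%, non-responder. Add 4 to 1: 1 − 8/16 = 50.0%, responder.

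These scores are invented. They show that status can change either way, not how often it would.

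**Omitting Induction baseline: simulation on assumed inputs.**

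- Data: 200,000 subjects, 2:1 active to placebo, five segments scored 0 to 12, Induction total at least 6. Week 10 = 0.5 × Induction baseline + noise (SD 1.5). Week 58 = a × Induction baseline + c × Week 10 + 0.8 if placebo + noise (SD 1.3).
- Missingness: 15% of subjects lack two of five segments at Week 58.
- Imputation: one regression draw on treatment, Week 10 segments and the observed Week 58 segments, without and then with Induction-baseline segments. Stratification factors were left out, and subjects were not selected on Week 10 response.

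Response rates (%) among affected subjects, and the share (%) whose derived response differs from complete data:

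| a, c | Active: without / with / complete data | Placebo: without / with / complete data | Misclassified: without / with |
|---|---|---|---|
| 0, 0.8 | 50.6 / 50.0 / 52.8 | 18.8 / 18.8 / 19.3 | 18.3 / 18.4 |
| 0.2, 0.6 | 36.5 / 35.9 / 38.2 | 9.1 / 7.8 / 8.1 | 18.1 / 17.7 |
| 0.4, 0.3 | 31.6 / 29.1 / 31.6 | 6.6 / 3.7 / 4.2 | 19.6 / 17.7 |
| 0.5, 0.2 | 25.1 / 21.0 / 23.0 | 4.1 / 2.0 / 2.3 | 17.4 / 15.1 |

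The largest shift is 25.1 − 21.0 = 4.1 points. With 15% affected, 0.15 × 4.1 = 0.6 point on the arm rate. In that row the treatment difference among affected subjects goes from 21.0 to 19.0, and 0.15 × 2.0 = 0.3 point overall.

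Adding Induction baseline lowers misclassification whenever Week 58 depends on it, and in those rows it brings the placebo rate closer to complete data. It does not always bring the active rate closer (third row). Under the worst-score rule the affected subjects' response rate was 0.0% in both arms in every row, so the choice between the two imputation models matters far less than the step from worst score to imputation.

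**The case against.** The strongest reply is that this is one sensitivity analysis with limited reach. Treatment failures, and subjects who leave early without a result, are set to non-response in every imputed dataset, so imputation decides the outcome only for the rest. The Maintenance model already contains the closest earlier endoscopy. All of that stands, and it is why the size is small.

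Several stronger readings are tempting, and the documents do not support them.

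- *This is the only check on the worst-score rule.* SAP 6.2.5.3 also plans a tipping-point analysis. The sample code in Appendix 8 imputes subject-level response from treatment and strata and does not vary segment scores, so it tests something different, but it is a planned check. SAP 6.2.4 adds counts of available segments and a listing with the reason for missingness where available.
- *Missing Induction-baseline segments have no model.* The Induction model includes baseline segment scores, and Maintenance subjects come from Induction. What is unstated is whether those imputations carry over.
- *Resected bowel will be scored.* No section says how the central reader codes a removed segment. SAP Appendix 5 says only that examined segments are given values. If a removed segment were coded 0, nothing would be imputed. The SAP's own example of a segment-level problem is stricture (6.2.3.3), where the bowel exists.
- *Every segment missing at baseline should be dropped, as in the primary analysis.* A sensitivity analysis may legitimately vary that rule, and dropping them all would stop it doing so. The case is clear only for bowel that does not exist.

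**Conclusion.** The point holds as a specification gap with an easy improvement. The Maintenance model leaves out the reference value of its own endpoint, and the handling of segments missing at Induction baseline is not stated. As written, Table 6-7 would also count an absent segment if it is coded as missing.

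The size is probably small: about 0 to 4 points among affected subjects, and about 0.6 point at most on an arm rate, if 15% of subjects lack two segments and the simulated dependence is realistic. Neither assumption comes from the documents. The number of subjects with a resected segment is not given, so the effect of the second gap cannot be sized; no direction or between-arm bias has been shown.

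A reader might infer that agreement or disagreement with the primary result could not be interpreted. That goes too far. The primary analysis, alpha and power are unaffected.

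**What to change.** 1. In SAP 6.2.5.3, add Induction-baseline segment scores to the Maintenance imputation model, alongside maintenance baseline and Week 58. With all three in one model, segments missing at Induction baseline can be imputed there. If the Induction-study imputations are to be carried over instead, say so.
2. In Table 6-7 and 6.2.5.3, exclude segments documented as surgically absent at Induction baseline from imputation and from the total at all visits, and state how the central reading codes them. Segments missing at baseline for other reasons can stay in the imputation.

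The cost is a few sentences of SAP text and one set of model variables already collected. It needs no new data and no change to alpha, power or the primary analysis. If the SAP is already final, SAP Section 1 provides for recording such changes in the clinical study report.
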